- **Specify objectives and hypotheses to be tested in the research project**

Aim 1: Pilot test, in a randomized controlled design (N=120, 60 in each group), the effect of *ED GOAL* administered by trained nurses on patient and caregiver ACP engagement one month after leaving the ED.

Hypotheses: ACP engagement (a composite outcome combining patient-reported and EMR outcomes) will significantly increase in those who received *ED GOAL* compared to usual care.

Aim 2: Identify the patient-perceived benefits and obstacles of ACP conversations after *ED GOAL* using semi-structured interviews (N~30).

[figure not shown]
Rationale: Most patients who underwent our intervention in prior studies expressed their gratitude and reported how helpful the intervention was in their lives. Yet, these perceived benefits (“opened my eyes about what I need to focus in my life”) may be difficult to capture using validated, quantitative instruments. Furthermore, we will also elicit patient-perceived barriers to completing the ACP conversations.

3. General Description of Study Design

- **Explain the basic study design, e.g., parallel group, randomized controlled trial, open-label single arm study, cross over, adaptive, etc.**

This is a two-armed, parallel-design, pre-/post-intervention assessment study. We will conduct a randomized controlled trial for *ED GOAL* on a cohort of 120 older adults with serious illness to collect patient-centered outcomes and determine preliminary efficacy on increasing ACP engagement (self-reported and/or in the electronic medical record) one month after leaving the ED. We will also conduct qualitative interviews with participants of *ED GOAL*.

- **Provide study schema as applicable (a schema is required for greater than minimal risk studies, and optional for minimal risk studies)**

4. Subject Selection

Describe sources of subjects and procedures for subject selection, including the following:

- **Inclusion/Exclusion Criteria**

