Trained RAs will use Epic to identify patients in the ED or the hospital 8am to 6pm Monday through Friday. To capture potential subjects that we may have missed, we will also review recent discharge list who might be eligible based on inclusion/exclusion criteria. Once a potential subject is identified, the trained RA will approach the treating clinician to see if the patient is eligible and have capacity to consent (if the potential subject is in the ED or in the hospital). The study procedure will pause whenever the study team is interrupted by clinical activities of the participants and resume when it is determined to be feasible again by the clinical team.

Enrollment procedures and cognitive impairment screening:

Our trained study clinician will review the eligibility criteria with the RA prior to engaging with the potential subject. If the potential subject is agreeable to learn more about our study verbally, the study clinician will administer a validated, delirium screening (3D-CAM).²⁵

If the patient is found to have no delirium, the study clinician will classify the patients based on known diagnosis of cognitive impairment or by administering a validated, cognitive impairment screening (MiniCog and/or Quick Dementia Rating System, QDRS).^{26,27} Depending on the cognitive impairment status, the patients and/or caregivers will be enrolled in the study (**Table 2**).

Table 2 Intervention target and outcome assessment		
Cognition status	Study participants	Outcome assessment
Normal (MiniCog >2 and/or QDRS 0-1)	Patient only	ACP engagement for patient + EMR
Mild cognitive impairment and mild dementia (MiniCog<3 and QDRS 2-12)	Patient and caregiver	ACP engagement for patient + ACP engagement for caregiver + EMR
Moderate and advanced dementia (MiniCog<3 and QDRS 13-30)	Caregiver only	ACP engagement for caregiver + EMR

Upon classification of patients by their cognitive status, informed consent will be obtained using a 4-item consent capacity checklist (see attached 4-item consent capacity checklist). For patients with known/documented moderate/severe dementia per medical record or self-report, we will approach the caregiver for enrollment and perform the 4-point consent capacity checklist. If the caregiver states that the patient can assent (e.g., verbal, able to comprehend, etc.), we will obtain an assent from the patient. Patients are not the subjects of this study.

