At this time, the study clinician will announce to the subject that the research procedure will begin.

- **A separate description for adults and children if applicable**
Not applicable.
- **The process for obtaining consent from non-English speakers if applicable**
Not applicable.
- **The process to determine capacity to consent and use surrogate decision makers if applicable**

We will conduct the following procedures to determine the capacity to consent:

For subjects with no known diagnosis of mild cognitive impairment or dementia on medical record, we will ask the treating clinicians (if subjects are in the ED or in the hospital) regarding their assessment of capacity to consent and clinical stability to approach the subject. Then, the study clinician will follow the procedures described above to classify the patients based on cognitive impairment status and use the 4-item capacity checklist for consent.

For subjects with a known diagnosis of mild cognitive impairment or mild dementia, we will ask the treating clinicians (if subjects are in the ED or in the hospital) regarding their assessment of capacity to consent and clinical stability to approach the subject. At the same time, we will confirm the availability of a caregiver to serve as a study partner. If caregiver is unavailable, the subject will be excluded. Then, the study clinician will follow the procedures described above to classify the patients based on cognitive impairment status and use the 4-item capacity checklist for consent.

For subjects with a known diagnosis of moderate to advanced dementia, the caregivers will be consented for the study (patients will not be the subjects of our study). We will use the 4-item consent capacity checklist.

- **Procedures to minimize undue influence to enroll, particularly if recruiting the investigators' own patients**
The study team will have no patient/clinician relationship with the potential subjects being approached in this study.

- **Describe post-consent intervention assignment and randomization method if applicable**

We will have three groups of participants based on cognitive ability for this study:

- 1) Patients with normal cognition
- 2) Patients with MCI or mild dementia + their caregivers (both are participants)
- 3) Caregivers of patients with moderate and advanced dementia (only the caregivers are the participants)

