Upon classification of eligible participants into the correct group above, we will randomly assign them into one of two arms of the study using block randomization of four using a computer-generated algorithm:

- 1) Intervention (*ED GOAL*)
- 2) Control (usual care)

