Describe plans for statistical analysis, including:

- **Statistical methods/data analysis plan**

Aim 1 quantitative data analysis:

We will conduct an intention-to-treat analysis. Since the primary outcome is mean change in self-reported ACP engagement, we do not expect differences among patients who are admitted vs. discharged. For our secondary outcome, we suspect that there is a propensity of more ACP documentation in patients who are hospitalized and missingness in patients who are primarily cared for at outside institutions. We will plan to use regression in subgroup analysis for ACP documentation to account for hospitalization status. In addition, we will perform sensitivity analyses to account for clustering by individual outpatient clinicians, palliative care consultations, and cognitive impairment status. We will also perform sensitivity analyses for survey respondents (e.g., patients vs. caregivers). We will compare patient demographics by study arm to assess randomization using bivariable analyses (t-test for continuous variables and chi-square for categorical variables). The mean changes in ACP engagement (primary outcome) at one month will be compared by study arms to estimate effect sizes. Within arms, we will use a one-sample binomial exact test of proportions for categorical outcomes (e.g., EMR documentation), and Wilcoxon signed ranks test for ordinal outcomes (e.g., ACP Engagement Survey) at baseline, after the intervention at one month. A p-value of 0.05 will be the significance threshold. To address missing data, I will conduct a secondary analysis using linear mixed models at baseline and one month. For qualitative outcomes,

Aim 2 qualitative data analysis:

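### The plan does not say whether the blocks of four are formed within the three cognitive groups, and the primary one-month comparison does not adjust for group

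*Combined protocol and SAP*

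**What the plan says.** The randomization item in Section 5 (Subject Enrollment) opens with "We will have three groups of participants based on cognitive ability for this study": patients with normal cognition, patients with mild impairment or mild dementia together with a caregiver, and caregivers alone where dementia is moderate or advanced. The allocation sentence follows. Once participants have been classified, "we will randomly assign them into one of two arms of the study using block randomization of four using a computer-generated algorithm". No stratification factor is named, and nothing is said about one list or several.

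Table 2 in the same section ties the group to the measurement. The first group gives the patient survey and the third the caregiver survey. For the middle group the entry is "ACP engagement for patient + ACP engagement for caregiver + EMR".

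Section 9 (Aim 1 quantitative analysis) compares mean change in ACP engagement at one month between arms and names no covariate. Cognitive group appears in this sentence: "we will perform sensitivity analyses to account for clustering by individual outpatient clinicians, palliative care consultations, and cognitive impairment status". The next sentence adds a sensitivity analysis by survey respondent, patients against caregivers.

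**The concern.** Cognitive group is more than an ordinary baseline covariate here, because it fixes the respondent and the instrument behind the primary score. Blocks of four on a single list balance the arm totals but not the groups. One arm could by chance hold more caregiver respondents than the other. Part of the observed difference in mean change would then reflect who was interviewed, if patients and caregivers change by different amounts.

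The trial's purpose is to estimate preliminary effect sizes for a later definitive trial, so the clarity of that one estimate matters. The group is recorded before allocation and could be balanced at almost no cost.

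**Working it through.** **Inputs from the plan.** Section 2, Aim 1: "Pilot test, in a randomized controlled design (N=120, 60 in each group". Section 5: blocks of four and three groups. Section 9: a conservative effect size of 0.25.

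**Assumptions.** The plan gives no group mix, so a group's share p is varied from 10% to 50%. A difference of 0.5 SD in mean change between respondent types is assumed for illustration.

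**The plan's own figure.** 120 / 4 = 30 complete blocks, each 2:2, which gives 60 and 60. The arm sizes are consistent with one list. The plan states no figure for balance within groups.

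**Imbalance with one list.** With 60 per arm and group membership independent of arm, the group's count in each arm is Binomial(60, p). The difference D between arms has mean 0 and SD = √(120 × p × (1 − p)).

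| Assumed share p | SD of D | P(group counts differ by 6 or more) |
|---|---|---|
| 10% | √10.8 = 3.3 | 9% |
| 15% | √15.3 = 3.9 | 16% |
| 20% | √19.2 = 4.4 | 21% |

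The probabilities come from enumerating the two binomials and agree with simulation. For a group with a 25% share, the SD is √22.5 = 4.7, and counts differ by 8 or more in about 11% of trials.

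Expressed as a share of each arm, the simulated 95th percentile of the absolute difference runs from 10.0 points (p = 10%) to 18.3 points (p = 50%).

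**Imbalance with a list per group.** Only the last, incomplete block can be unbalanced, so counts within a group differ by at most 2. The simulated 95th percentile is 1.7 to 2.9 points.

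**Effect on the primary estimate.** The shift in the arm difference equals the imbalance in share times the difference in mean change between respondent types.
- At p = 10%: 0.100 × 0.5 = 0.05 SD.
- At p = 50%: 0.183 × 0.5 = 0.09 SD.
- Standard error of the arm difference: √(2/60) = 0.18 SD.
- Against the effect of 0.25, read as a standardised mean difference: 0.05/0.25 = 20% and 0.09/0.25 = 36%.

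**Average loss of precision without adjustment.** The variance rises by the factor 1 + p(1 − p) × 0.5².
- At p = 10%: 1 + 0.09 × 0.25 = 1.0225, so the standard error is about 1% larger.
- At p = 50%: 1 + 0.25 × 0.25 = 1.0625, so it is about 3% larger.

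The average loss is therefore small. The larger cost is in reading one particular result when the group mix happens to be uneven.

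**The case against.** The allocation sentence may already mean blocks within group. The groups are listed under the randomization item, and assignment is said to follow classification into them. A reader might infer that allocation is unstratified, but the text is silent on this and supports either reading. What stands is that the plan does not say.

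A reader might also infer that arm is confounded with respondent. That does not follow. Allocation is random under either scheme, the expected difference in group mix is zero, and the standard error of the unadjusted comparison already reflects chance imbalance.

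Three features of the plan reduce the concern further. The outcome is change from baseline, which removes differences in level between instruments, though not differences in how much respondents change. The caregiver survey is described as measuring the same processes and behaviours as the patient survey. Sensitivity analyses are planned for both cognitive status and respondent type. These analyses do address the question, but only outside the primary comparison.

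Nor do the numbers show that the caregiver-only group would be too lopsided to describe by arm. A difference of 6 among about 18 people is 12 against 6, and about 84% of trials at a 15% share would be better balanced than that.

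Finally, adjusting for group would deal with most of the chance imbalance without any change to randomisation. That is fair, and it is half of the fix below.

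**Conclusion.** The point holds as a gap in specification with a cheap improvement. The plan leaves open whether blocks are formed within cognitive group, and its primary comparison does not use a factor that decides respondent and instrument.

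If one list is used, a difference of 6 or more in the caregiver-only group occurs in about 9% to 21% of trials at assumed shares of 10% to 20%. A 95th-percentile imbalance would move the arm difference by about 0.05 to 0.09 SD under the assumed 0.5 SD difference in change. That is less than the 0.18 SD standard error, but not negligible against an effect of 0.25.

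The consequence is some loss of precision and interpretability, not bias. The sizes depend on group shares and a between-respondent difference that the plan does not give. If lists per group were always intended, the allocation half of the point is met by saying so; the missing adjustment remains.

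**What to change.** - **Section 5, randomization item:** state that a separate permuted-block list is used for each of the three cognitive groups. If that was the intention, this is only a clarification.
- **Section 9, Aim 1:** include cognitive group as a factor in the primary one-month comparison of mean change. Keep the respondent-type analysis as a sensitivity analysis.

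The cost is three lists in place of one in the existing algorithm and one added factor in the model. The group is already recorded before allocation, so no new data are needed. Up to three blocks may be incomplete at the end, so overall arm sizes may differ by a few.

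This change does not settle how patient and caregiver scores are combined when both respond. That needs its own statement.

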Participants will only consist of patients who meet the inclusion/exclusion criteria in **Table 1**. For eligible patients who have mild cognitive impairment (MCI) or mild dementia (as shown by cognitive impairment assessment), both the patient and the patient’s caregiver will be enrolled as subjects in the study. For patients with moderate to severe dementia, the caregivers will be the study participants, and no involvement of the patients will occur. We will determine the potential subject’s cognitive status by review of medical records and screening described in the “Subject Enrollment” section below.

The caregivers are defined as health care proxy or next of kin (when health care proxy has not been appointed). Patients without competency who has court-appointed legal guardians are excluded from this study given the nature of ACP conversations for this group is largely different from ordinary patient/caregivers. Given that this is a minimal risk study (i.e., patients and caregivers are routinely experiencing ACP conversations in their clinical encounters), we will obtain verbal consent/assent using the study information sheet.

Table 1 Patient eligibility criteria	
Inclusion	Exclusion
1. ≥50 years of age AND ≥1 Serious illness* OR ED clinician would not be surprised if patient died in the next 12 months (a validated prognostic sign) ^{23,24}	1. Acute physical or emotional distress
2. English-speaking	2. Determined by treating or study clinician not to be appropriate
3. Capacity to consent	3. Clearly documented goals for medical care** (Unless the treating or study clinician recommends that the intervention is clinically indicated)
a. Patient with mild cognitive impairment or mild dementia with capacity to consent (requires a caregiver/study partner to enroll)	4. Delirium (assessed using 3D-CAM)
b. Caregiver of patient with moderate/severe dementia with capacity to consent	5. Already enrolled in this study
	6. Unable/unwilling to schedule the follow-ups on the calendar

	7. Receive both the outpatient care for serious illness and primary care outside of the MGB system

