*NYHA Stage III/IV congestive heart failure, chronic obstructive lung disease on home oxygen, chronic kidney disease on dialysis, or metastatic solid tumor cancer. In addition, patients with NYHA Stage I/II congestive heart failure, chronic obstructive lung disease not on home oxygen, chronic kidney disease not on dialysis will be included if recent hospitalization in the last 12 months exists.	**e.g., MOLST, medical order for life-sustaining treatment, documented serious illness conversations in clinician notes within the last 3 months, etc.

• **Local Recruitment Procedures:**

Explain in detail the methods and procedures you will use to recruit participants. Describe in a step-by-step procedure below:

- **How individuals are identified for recruitment including description of use of recruitment materials such as flyers, brochures, advertisements, letters, etc.**

Our research team will review the medical records in Epic to identify the potential subjects to approach in this study. To identify potential subjects in the ED, we will review the ED patient lists Monday to Friday between 8am to 6pm. To capture potential subjects we missed during this screening period, we will also review medical records of patients who visited the ED in the last 10 days so that we can enroll them virtually after leaving the ED/hospital (if admitted).

- **Who is responsible (role on research team) for identifying and recruiting individuals**

Trained RAs will search through the medical records to find potential subjects meeting our inclusion and exclusion criteria. The study clinician consenting the subjects will double check the eligibility criteria prior to consent.

- **When individuals are recruited**

Subjects will be approached for recruitment at the time of ED visit, during their hospitalization after the ED visit, or within 10 days of leaving the ED.

- **Where individuals are recruited**

We will recruit subjects in the ED, ED observation unit, or hospital floor at Brigham and Women’s Hospital, Massachusetts General Hospital, and Brigham and Women’s Faulkner Hospital.

We will make every attempt to enroll/approach the patient in the ED. We will follow the following steps:

1. When potential subjects are identified in the ED, clinical appropriateness is assessed with the treating clinicians;
2. The treating clinicians will introduce the study and obtain permission for our research team to approach the subject in the ED; and

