6. STUDY PROCEDURES

Provide detailed description of all study visits, procedures, and data collections, including:

- **Description of each study visit and procedures at each visit (include a schedule/table of study procedures)**

Initial enrollment (~30 to 60 minutes total):

After the consent, our trained study clinician will administer the intervention to the participant in-person, on the phone, or over zoom depending on participant preference. After the intervention is completed, the RA will obtain post-enrollment questionnaires and also schedule dates/times for the follow-up appointments. With participants' permission, the study clinician will document the clinically important findings elicited from the participant (e.g., preferences for end-of-life care goals) in Epic's ACP module and also send an email regarding the findings to patient's outpatient clinicians within Mass General Brigham health system via secure email. The study team will also provide the post-enrollment patient handout (see attachment) to the participants. All participants in the intervention arm will receive the same intervention and follow-up procedures.

Follow-up appointments (~30 to 45 minutes each):

During the scheduled follow-up appointments on the phone/zoom, our RA will administer surveys to assess for the outcomes. In addition, if the participants report that they have not had conversations with their outpatient clinicians about ACP, our study clinician will conduct brief coaching to overcome the obstacles participants might be facing in this process and also document clinically relevant information in Epic to notify to the outpatient clinician.

Table 3 Study visits		
Study visit	Intervention	Outcome assessment
Initial enrollment	ED GOAL	Post-enrollment survey

1-month follow-up	ACP navigation coaching (as needed)	Follow-up patient-reported outcomes surveys
3-month follow-up	ACP navigation coaching (as needed)	Follow-up patient-reported outcomes surveys
6-month follow-up	ACP navigation coaching (as needed)	Follow-up patient-reported outcomes surveys

- **Description of study drugs, devices, or other interventions/exposures administered, including:**

- **Dose, method of administration, schedule of administration, dose modifications**

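### One stated block size of four, with no concealment described, makes up to one third of assignments foreseeable by staff who also judge eligibility, if they know the allocation history

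*Combined protocol and SAP*

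**What the plan says.** The randomisation plan is one sentence in Section 5, under the post-consent assignment heading. Once participants are classified into one of three cognitive groups, they are allocated to ED GOAL or usual care: "Upon classification of eligible participants into the correct group above, we will randomly assign them into one of two arms", "using block randomization of four using a computer-generated algorithm". Section 2 gives the size as "N=120, 60 in each group". The protocol does not say whether the block size varies, who holds the list, how an assignment is released, or whether each cognitive group or hospital has its own list. It mentions no blinding.

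The study clinician's role is described in three places:

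- **Checking eligibility.** Section 4 states: "The study clinician consenting the subjects will double check the eligibility criteria prior to consent". Section 5 adds: "Our trained study clinician will review the eligibility criteria with the RA prior to engaging with the potential subject".
- **Discretion.** In Table 1, exclusion 2 reads "Determined by treating or study clinician not to be appropriate". Exclusion 3 (goals already documented) carries an override: "Unless the treating or study clinician recommends that the intervention is clinically indicated".
- **Delivery.** Section 6, Initial enrollment, states that after consent "our trained study clinician will administer the intervention to the participant".

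**The concern.** Assignment follows consent, but the discretion over who is approached and enrolled is used before it. With a constant, known block size, someone who has followed the list can work out how a block must end. A computer-generated list does not prevent that. If the foreseen arm influences who is judged suitable, or who is let through the documented-goals exclusion, the arms may differ at entry in their readiness for advance care planning (ACP). That trait is close to what the trial measures: ACP engagement and new documentation in the medical record. Section 1 says the findings will support a larger trial, so a distorted effect estimate would carry forward.

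Two features of Section 4 add to the opportunity. Recruitment is to be adjusted when each arm nears half its target, so someone must track enrolment by arm. Patients may also be approached in the ED, during admission or up to 10 days after leaving the ED, which gives some latitude over order.

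**Working it through.** The protocol states no predictability figure, so there is none to reproduce.

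**Inputs.** Block size 4 and two arms (Section 5); 120 participants, 60 per arm (Section 2). Equal allocation within a block gives 6 equally likely orders: AABB, ABAB, ABBA, BAAB, BABA and BBAA.

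**Certain assignments, full history known.** An assignment is certain once one arm is used up within the block.
- Positions 1 and 2: never certain.
- Position 3: certain when the first two match (AABB, BBAA), so 2/6 = 1/3.
- Position 4: always certain.
- Expected per block: 1/3 + 1 = 4/3. Share: (4/3)/4 = 1/3, that is 8 of 24 positions, or 40 of 120.

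**Correct guesses, full history known.** The guesser always picks the arm used less so far in the block.
- Position 1: 1/2. Position 2: 2/3. Position 3: (1/3)(1) + (2/3)(1/2) = 2/3. Position 4: 1.
- Sum 17/6. Share: (17/6)/4 = 17/24 = 70.8%.

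**Partial history.** Assume one shared list and c clinicians, each equally likely to enrol any participant. Each knows the position in the block but only their own patients' arms. Certainty then requires that both earlier assignments to the used-up arm were the clinician's own, which has probability 1/c². The certain share is (1/3)/c²:
- c = 2: 1/12 = 8.3%
- c = 3: 1/27 = 3.7%
- c = 5: 1/75 = 1.3%

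Simulation gave 8.3%, 3.8% and 1.2%. The protocol does not state the number of clinicians.

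**Varying block sizes.** 4,000 simulated lists of 120, with the set of sizes and all past assignments known to the guesser but the block boundaries unknown:

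| Block sizes | Certain | Guessed correctly |
|---|---|---|
| 4 only (exact) | 33.3% | 70.8% |
| 4, 6 | 5.5% | 69.2% |
| 4, 6, 8 | 2.3% | 67.9% |

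**What it could do to the estimate (assumed illustration).** If enrolled patients differed by s SD according to the guessed arm, the bias would be (2 × 17/24 − 1)s = 0.42s. For s = 0.1, 0.25 and 0.5 that is 0.04, 0.10 and 0.21 SD. The protocol's conservative effect size is 0.25 (Section 9). Nothing in the documents gives a value for s.

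**The case against.** A reader might infer four stronger things that the documents do not support.

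- **That one third of assignments are certain as a matter of fact.** This needs the block size, the block start and every earlier assignment on the list to be known. It is an upper figure.
- **That the person delivering ED GOAL sees every assignment.** Section 6 (Intervention fidelity) refers to study clinicians in the plural, and Section 4 names three hospitals. Each clinician learns the arm of their own participants; nothing says assignments are shared.
- **That the study clinician is the only gatekeeper.** Both Table 1 criteria name the treating or the study clinician. Research assistants do the search, and for patients in the ED, treating clinicians assess appropriateness and give permission to approach. Nothing suggests that treating clinicians know the allocation history. The study clinician can still use either criterion.
- **That the analysis cannot correct any resulting imbalance.** Readiness is part of the ACP engagement survey, which the Section 6 measures table lists at baseline. Section 9 compares mean change and adds a mixed model using baseline and one month. Measured imbalance is therefore at least partly handled. Unmeasured differences could remain. The Section 6 visit table also shows only a post-enrollment survey at the first visit, so it is unclear whether a baseline measure precedes assignment.

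It can also be said that small blocks are a reasonable way to keep 120 participants balanced, and that this is a pilot which the protocol says is not powered for significance. Both are fair. Neither is a reason to leave the list predictable, because the pilot's effect estimates are meant to inform a later trial.

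**Conclusion.** The concern holds in limited form. The plan combines a single stated block size, a usual-care control, no described blinding or concealment, and a clinician role that has both eligibility discretion and knowledge of at least some assignments. With full knowledge of the list, up to one third of assignments are certain and 71% can be guessed. With own-patient knowledge on a shared list, certainty falls to about 8% for two clinicians and 4% for three. If each cognitive group has its own list, the one-third figure applies within each list over complete blocks.

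That the block size is constant and the trial unblinded are inferences: one size is given, no blinding is described, and whoever delivers ED GOAL must know the arm. The figures measure predictability. They do not show that selection bias will occur, or how large it would be.

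**What to change.** In Section 5, replace the words "using block randomization of four using a computer-generated algorithm" with a plan that states the following:

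1. Block sizes vary at random (for example 4 and 6, or 4, 6 and 8), and recruiting staff are not told the sizes.
2. The list is generated and held in REDCap, which Section 7 shows is already in use. The plan also states whether each cognitive group or hospital has its own list.
3. Running allocation history, including the per-arm counts needed for the Section 4 recruitment check, is kept from those judging eligibility where feasible.
4. Each assignment is released only after eligibility (including both discretionary judgements), consent and the baseline survey are recorded.

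Varying the sizes removes most of the certainty but little of the guessing, so item 1 is not enough alone. Item 4 stops eligibility being revised once the arm is known, but it does not stop a prediction made beforehand; item 3 is aimed at that.

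The cost is randomisation set-up and a few sentences of protocol. Sample size and visits do not change. The downside is a slightly larger possible imbalance at the end of a list: up to four participants with an incomplete block of eight, against two with a block of four. With separate lists this would apply within each cognitive group, where small groups would feel it most. Using sizes 4 and 6 only limits it to three, with certainty at 5.5%.
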